The myPACE trial demonstrated that personalized accelerated pacing at rest, with a median lower rate of 75 bpm compared to the standard setting of 60 bpm, led to improvements in quality of life, NT-proBNP levels, physical activity, and device-detected atrial fibrillation (23). In contrast, the RAPID-HF study investigating pacemaker implantation with rate-responsive pacing in HFpEF patients with CI found no significant improvement in $\text{VO}_{2\text{peak}}$ and VO_2 at VAT (24). This lack of effect may be attributed to several factors, including the small sample size ($n = 29$), the absence of accelerated pacing at rest, and a suboptimal chronotropic response during exercise. Specifically, excessive heart rate increases may compromise CO in HFpEF due to their impaired diastolic filling and a blunted pressure-volume relationship (25-27). Conversely, an insufficient heart rate rise may fail to adequately enhance chronotropic function or reduce PCWP, thereby limiting hemodynamic benefit. To address these uncertainties, we aim to investigate hemodynamic responses across multiple pacing frequencies. Moreover, this study has focused on high-intensity exercise, evaluating outcomes beyond the anaerobic threshold. In contrast, our study targets low-intensity exertion.

Shear wave velocity as a marker of ventricular stiffness in HFpEF

An additional parameter we will evaluate in this study is shear wave velocity (SWV). This imaging technique provides insights into myocardial stiffness by assessing the propagation speed of naturally occurring myocardial shear waves following mitral valve closure. A study by Salerno et al. demonstrated that higher pacing frequencies are associated with increased SWV, indicative of

elevated ventricular stiffness (28). However, these findings were observed in a population without HFpEF. In patients with HFpEF, who are characterized by increased ventricular stiffness and a steep EDPVR, the effects of pacing on ventricular stiffness and SVV is unknown. These insights may aid in the pathophysiological understanding of pacing strategies designed to improve diastolic function and exercise tolerance in patients with HFpEF.

Study rationale and objective

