2.3 Secondary endpoints

The secondary endpoints are:

- The change in CO at the pacing frequency corresponding to the greatest reduction in PCWP compared to the intrinsic heart rate
- The change in SV at the pacing frequency corresponding to the greatest reduction in PCWP compared to the intrinsic heart rate
- The change in peripheral oxygen extraction at the pacing frequency corresponding to the greatest reduction in PCWP compared to the intrinsic heart rate
- The change in SWV for each pacing frequency. The SWV at the intrinsic heart rate is defined as the average of the SWV at the intrinsic heart rate heart rate before and after each pacing step.

Cardiac output is measured via the direct Fick principle, dividing VO_2 by the peripheral oxygen extraction (SaO_2 - SvO_2). SV is calculated as CO divided by HR.

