- During the study protocol, pacemaker settings will be actively adjusted to alternate between intrinsic rhythm (back-up pacing mode) and accelerated pacing at various frequencies. Previous studies involving stepwise increases in pacing rates in patients with HFpEF have all been conducted safely (26, 36-39). Nevertheless, accelerated pacing may pose certain physiological risks, including a reduction in diastolic filling time, potentially leading to diastolic underfilling and subsequent blunting of the Frank-Starling mechanism. These changes may contribute to hypotension and orthostatic symptoms (40). Pacing frequency will be limited to the age-predicted maximum heart rate (APMHR), preventing supraphysiological rates in patients with elevated resting heart rates. Furthermore, abrupt transitions between pacing OFF and ON settings may cause palpitations, dyspnoea, or

dizziness. To avoid excessive heart rate fluctuations, the backup pacing rate during OFF episodes in exercise will be increased to approximately 20 bpm below the intrinsic heart rate at that level of exertion, rather than reverting to the resting backup mode. To mitigate potential risks, only patients in stable sinus rhythm will be included. All pacemaker adjustments will be performed under supervision of a cardiologist. Transitions between pacing modes will occur gradually, with continuous ECG and hemodynamic monitoring throughout. The study will take place in a fully equipped medical environment with a defibrillator and trained staff present at all times. In case of any signs of hemodynamic compromise, pacing will be immediately restored to a safe backup mode.

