6.2 Statistical analysis

This is a prospective, single-arm, multicentre, interventional study in which each patient serves as their own control:

- A two-sided significance level of 0.05 will be used for all statistical tests.
- Data will be analyzed using Python, SPSS and Stata statistical software.
- Descriptive statistics of baseline variables will be used to summarize baseline characteristics.
 - Categorical variables will be presented as number and percentage.
 - Continuous variables will be presented as mean \pm standard deviation or median with interquartile range, depending on the Shapiro-Wilk test for normality.
- Comparison of hemodynamic parameters (PCWP, CO, SV, peripheral oxygen extraction) and SVV will be performed using paired student t-test or Wilcoxon-Mann Whitney test whichever will be appropriate.
- Pearson's or Spearman's correlation coefficients, whichever will be appropriate, will be computed to assess the relationship between changes in PCWP and changes in SVV

Endpoint	Statistical analysis methods
Primary	paired student t-test or Wilcoxon-Mann Whitney test
Secondary	paired student t-test or Wilcoxon-Mann Whitney test
Exploratory	descriptive statistics, Pearson's or Spearman's correlation coefficient

7 Data handling

A study-specific Data Management Plan (DMP) will be developed by the Sponsor providing a.o. further details on data flows, data handling, processing and discrepancy management.

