14. The Data Processor must reasonably assist the Data Controller with meeting the other obligations that may be incumbent on the Data Controller according to European Union or Member State law where the assistance of the Data Processor is implied, and where the assistance of the Data Processor is necessary for the Data Controller to comply with its obligations. This includes, but is not limited to, at the request to provide the Data Controller with all necessary information about an incident under 10) (ii), and all necessary information for an impact assessment in accordance with Article 35 and Article 36 of the GDPR.

Subprocessor:

15. The Data Processor may only engage a subprocessor, with prior specific or general written consent from the Data Controller. The Data Processor undertakes to inform the Data Controller of any intended changes concerning the addition or replacement of a subprocessor by providing a reasonable prior written notice to the Data Controller. The Data Controller may reasonably and in a duly substantiated manner object to the use of a subprocessor. The Data Processor must inform the Data Controller in writing of the discontinued use of a subprocessor.

16. Prior to the engagement of a subprocessor, the Data Processor shall conclude a written agreement with the subprocessor, in which at least the same data protection obligations as set out in this DPA shall be imposed on the subprocessor, including obligations to implement appropriate technical and organizational measures and to ensure that the transfer of personal data is done in such a manner that the processing will meet the requirements of the applicable law.

17. The Data Controller has the right to receive a copy of the relevant provisions of Data Processor's agreement with the subprocessor related to data protection obligations. The Data Processor shall remain fully liable to the Data Controller for the performance of the subprocessor obligations under this DPA. The fact that the Data Controller has given consent to the Data Processor's use of a subprocessor is without prejudice for the Data Processor's duty to comply with this DPA.

15 APPENDIX 3: Detailed description of the study protocol in resting conditions

The following section provides a stepwise description of the pacing protocol performed at rest (Figure 3):

- Pacing-off:
 - Measurement of SWV
 - Measurement of PCWP
- Pacing-on:

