 - Set the pacemaker to DDD mode with a lower rate of **20** bpm above the intrinsic heart rate, rounded to the nearest decimal
 - Adjust AV-delay to the optimal setting and measure shear wave velocity
 - 10 seconds after AV delay optimization: PCWP measurement
- Pacing-off:
 - Reprogram the pacemaker to back-up mode
 - Measurement of SWV
 - 10 seconds after pacemaker reprogramming: PCWP measurement
- Pacing-on
 - Set the pacemaker to DDD mode with a lower rate of **40** bpm above the intrinsic heart rate, rounded to the nearest decimal
 - Adjust AV-delay to the optimal setting and measure shear wave velocity
 - 10 seconds after AV delay optimization: PCWP measurement
- Pacing-off:
 - Reprogram the pacemaker to back-up mode
 - 10 seconds after pacemaker reprogramming: PCWP measurement
- Pacing-on:
 - Set the pacemaker to DDD mode with a lower rate of **60** bpm above the intrinsic heart rate, rounded to the nearest whole number
 - Adjust AV-delay to the optimal setting and measure shear wave velocity
 - 10 seconds after AV delay optimization: PCWP measurement
- Pacing-off:
 - Reprogram the pacemaker to back-up mode
 - Measurement of SWV
 - 10 seconds after pacemaker reprogramming: PCWP measurement
 - After 4 respiratory cycles: collection of arterial and mixed venous blood samples
- Pacing-on
 - Set the pacemaker to DDD mode with a lower rate corresponding to previously determined rate with the greatest reduction in PCWP
 - 10 seconds after pacemaker reprogramming: PCWP measurement
 - After 4 respiratory cycles: collection of arterial and mixed venous blood samples
- Pacing-off: reprogram to pacemaker back-up mode

HR, VO₂, RER and will continuously be measured.

Each pacing-off (DDD 40 back-up pacing mode) and pacing-on (temporary DDD pacing via programmer) period will take 40 seconds.

The optimal AV-delay will be determined via iterative evaluation of the mitral valve inflow by transthoracic echocardiography. This will be followed by SWV measurements, performed over a 12-second period.

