PCWP will be measured as the average end-expiratory value over four consecutive respiratory cycles, following a 10-second period to allow for hemodynamic stabilization. By comparing each PCWP value to the average of the PCWP measured during the pacing-off periods immediately before and after the pacing-on phase, we aim to minimize the impact of spontaneous hemodynamic variability and carry-over effects (41). The heart rate associated with the greatest reduction in PCWP will be repeated as the final pacing-on step, during which CO will be measured by collecting arterial and mixed venous blood samples (direct Fick principle). If two pacing rates result in an equal reduction in PCWP, the lower pacing rate will be selected. If no reduction in PCWP is observed with accelerated pacing, the heart rate corresponding to the smallest increase in PCWP will be selected for the final pacing-on period instead. In this final step, PCWP will be measured again to verify that it remains consistent with the initial PCWP at the same pacing rate. Only the initial PCWP measurement at the optimal pacing rate will be used in our analyses assessing changes in PCWP compared to the intrinsic heart rate.

The pacing rate will never exceed the APMHR, calculated based on Takana's equation (42). If this threshold would be reached, the protocol will be stopped at the pacing step prior to exceeding the APMHR, only followed by the final pacing step in which the pacing rate associated with the greatest reduction in PCWP is repeated.

16 APPENDIX 4: Detailed description of the study protocol during exercise

The following section provides a stepwise description of the pacing protocol performed during exercise (Figure 4):

- Pacing-off:
 - Measurement of SWV
 - PCWP measurement after 10s of cycling
- Pacing-on:
 - Set the pacemaker to DDD mode with a lower rate of **10** bpm above the intrinsic heart rate, rounded to the closest decimal and with dynamic AV-delay settings
 - Evaluate mitral inflow pattern on echocardiography for evidence of E-wave truncation; if truncation is observed, the AV-delay will be adapted accordingly.
 - Non-invasive measurement of BP
 - Measurement of SWV
 - 10s after the last change in pacemaker settings: PCWP measurement
- Pacing-off:
 - Reprogram the pacemaker to back-up mode
 - Measurement of SWV
 - 10 seconds after pacemaker reprogramming: PCWP measurement
- Pacing-on:

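### After each return to back-up pacing, Appendices 3 and 4 list shear wave velocity ahead of the 10-second PCWP point with no settling time of its own, so the reference for a secondary endpoint may carry residual pacing effect

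*Combined protocol and SAP*

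**What the plan says.** Appendix 3 opens with "The following section provides a stepwise description of the pacing protocol performed at rest", and Appendix 4 uses the same format for exercise. In the pacing-off periods after +20 and +60 bpm at rest, and after +10, +30 and +50 bpm at both 10 W and 25 W, the order is the same: return to back-up pacing, SWV, then "10 seconds after pacemaker reprogramming: PCWP measurement". The rest period after +40 bpm lists PCWP but no SWV.

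Appendix 3 explains that PCWP is averaged over four breaths "following a 10-second period to allow for hemodynamic stabilization". It states no wait for SWV. The only SWV duration given comes after the sentence on AV-delay optimisation: "This will be followed by SWV measurements, performed over a 12-second period". Each pacing-on and pacing-off period lasts 40 seconds.

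Section 2.3 makes the SWV change at each pacing rate a secondary endpoint: "The SWV at the intrinsic heart rate is defined as the average of the SWV at the intrinsic heart rate" before and after each step. Section 6.2 adds correlation coefficients that "will be computed to assess the relationship between changes in PCWP and changes in SVV" (SVV is read here as SWV).

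**The concern.** The off-period SWV reading is meant to represent the intrinsic rhythm. Section 1 describes SWV as "assessing the propagation speed of naturally occurring myocardial shear waves following mitral valve closure", and describes HFpEF hearts as having a steep end-diastolic pressure-volume relation. SWV could therefore change while filling readjusts after the rate falls. The protocol thinks PCWP needs 10 s for this, yet the listed order takes SWV before that time is up.

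Pacing effect left in an off reading moves the reference towards the paced value and shrinks the measured change. More patients would not remove this. Averaging the readings before and after a step, which Appendix 3 offers against carry-over, does not help when the carry-over sits in the reference readings themselves. The shrinkage differs by rate, so it would distort the relation between rate and stiffness that the study wants to describe. The exploratory correlation would pair a settled PCWP change with an SWV change whose reference is not settled.

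**Working it through.** The plan has no SWV effect size, SD or power figure to reproduce. The sample size in section 6.1 concerns PCWP only.

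**1. Readings affected (Appendices 3 and 4).**
- Rest: 3 off readings (start, after +20, after +60), of which 2 follow pacing.
- Exercise: 4 per stage (start, after +10, +30, +50), of which 3 follow pacing; two stages.
- Total: 3 + 4 + 4 = 11, of which 2 + 3 + 3 = 8 follow pacing.
- Contrasts: 3 rates × 3 conditions = 9. At rest, +20 uses the starting reading and one affected reading; +40 has only the affected reading before it; +60 has only the affected reading after it. In exercise, +10 uses the starting reading and one affected reading; +30 and +50 use two affected readings each. All 9 include at least one.

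**2. Timing.** PCWP starts 10 s after the switch and SWV is listed before it. A 12-s reading cannot finish first (12 > 10). Started at 0 s, it has 10 of its 12 s in the stabilisation window and overlaps PCWP by 2 s. Started at 5 s, it has 5 of 12 s in the window. Any start that keeps the listed order falls inside the window.

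**3. Residual share r.** Assume a one-action switch, exponential settling with time constant τ, and SWV averaged over 12 s from start time s:

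r = (τ/12) × e^(−s/τ) × (1 − e^(−12/τ))

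Assumed settling of 95% in 5 to 10 s gives τ of about 1.67 to 3.3 s (τ ≈ settling time / 3). The upper end borrows the protocol's own PCWP wait.

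| SWV start after switch | τ = 1.67 s | τ = 3.3 s |
|---|---|---|
| 0 s | 0.139 | 0.268 |
| 3 s | 0.023 | 0.108 |
| 5 s | 0.007 | 0.059 |
| 10 s | <0.001 | 0.013 |

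With an instant response, r = 0.

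**4. Effect on the contrasts.** Let the true SWV change be proportional to the rate increment, with the paced reading settled. An affected reading carries r times the effect of the rate just before it. Measured/true, with the worst case r = 0.268:

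| Contrast | Formula | Result |
|---|---|---|
| Rest +20; exercise +10 | 1 − r/2 | 0.87 |
| Rest +40 | 1 − r × (20/40) | 0.87 |
| Rest +60 | 1 − r | 0.73 |
| Exercise +30 | 1 − r × (10/30 + 1)/2 | 0.82 |
| Exercise +50 | 1 − r × (30/50 + 1)/2 | 0.79 |

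With r = 0.108 (3-s start, slower lag) the extremes are 1 − 0.108 = 0.89 (rest +60) and 1 − 0.054 = 0.95 (rest +20 and +40, exercise +10).

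**5. Does a later SWV fit?** Four breaths take 12 to 20 s at an assumed 20 to 12 breaths/min. With SWV and PCWP both starting at 10 s, the period needs 10 + 12 = 22 s to 10 + 20 = 30 s of its 40 s. PCWP alone already needs that long.

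**The case against.** The SWV line in the off periods has no clock. Figures 3 and 4 are not shown and might give one, so the start time is inferred from list order. Staff could pause before recording, and even a 3-s pause brings r down to 2-11%. The 12-s duration is stated for the AV-optimised step and only carried over here. The settling time is assumed: a 10-s margin for wedge pressure is not evidence that SWV needs 5 to 10 s, and r may be zero. All of this stands and limits what can be said about size. It does not supply the missing wait: nothing tells staff at two sites to pause, and the listed order says the opposite.

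Stronger readings are tempting but unsupported:
- A reader might infer that later rates in general keep only 73% of the true change, so that a contrast with 80% power at n = 16 drops to 54%. That needs equal true effects at every rate. Section 1 cites SWV rising with pacing frequency, though outside HFpEF; with proportional effects 73% applies only to rest +60, and the other later-rate contrasts keep about 79-87%, all at the worst-case r. SWV also has no power target.
- A reader might combine the finding with section 5.3.2, "Transitions between pacing modes will occur gradually, with continuous ECG and hemodynamic monitoring throughout", and add a ramp to the SWV window. No ramp length is given anywhere, and the appendices describe a plain reprogramming step, so any figure would be invented.
- A reader might extend the point to PCWP. PCWP keeps its 10-s wait.

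**Conclusion.** The concern holds as a weakness in the measurement sequence for a secondary endpoint. Carried out as listed, 8 of 11 off-period SWV readings begin inside the protocol's own stabilisation window, and no SWV contrast avoids them. The direction is towards a smaller SWV change, by amounts that differ between rates. The size cannot be fixed from the documents. For a one-action switch it runs from nothing, through about 1-11% residual with a 3- to 5-s start, to 14-27% with an immediate start. The non-zero figures rest on assumed 95% settling in 5 to 10 s, a 12-s off reading and a settled paced reading. The primary endpoint and the sample size are unaffected. This is a cheap improvement worth making, not a threat to the trial's main result.

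**What to change.** In the pacing-off steps of Appendices 3 and 4, replace the separate SWV and PCWP lines with one instruction: start both PCWP and SWV 10 s after the final pacemaker setting change. Make Figures 3 and 4 agree. Under the same assumed lags this lowers the residual share to at most 1.3%.

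The 40-s periods stay as they are. The costs are practical: echo and wedge are recorded simultaneously for the full 12 s, including during cycling, where the listed order (SWV starting at the switch) overlaps them by about 2 s. In the last off period of each condition, 40 − 30 = 10 s to 40 − 22 = 18 s remain for the arterial and mixed venous samples, the same as PCWP timing leaves now.
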